15.8.2.2. Time to Complete TMA Response

For the secondary efficacy endpoint of time to Complete TMA Response, Kaplan-Meier cumulative distribution curves will be generated along with 2-sided 95% CIs. The corresponding summary table will present the cumulative distribution function (CDF) estimate, the number of patients at risk, the number of patients responding, and the number of patients censored at each postbaseline time point. The table will also present first quartile, median, and third quartile, along with corresponding 2-sided 95% CI, of time to complete response.

15.8.2.3. Complete TMA Response Status Over Time

Complete TMA Response will also be summarized over time by presenting the number and proportion of responders along with a 2-sided 95% CI for each postbaseline time point.

15.8.2.4. eGFR Value and Change from Baseline

Kidney function evaluated by eGFR will be summarized at baseline and each postbaseline time point using descriptive statistics for continuous variables for the observed value as well as the change from baseline. A value for eGFR will be imputed for patients requiring dialysis for acute kidney injury. A mixed model for repeated measures (MMRM) with the fixed, categorical effect of visit and fixed, continuous effect of the baseline value as covariates may be fit to test whether changes differ from zero at each time point.

15.8.2.5. CKD Stage

CKD stage ([Appendix J](#)) will be summarized over time by presenting the number and proportion of patients that improved (excluding those with Stage 1 at baseline as they cannot improve), worsened (excluding those with Stage 5 at baseline as they cannot worsen), and stayed the same compared to CKD stage at baseline. Stage 5 will be considered the worst category, while stage 1 will be considered the best category. A 2-sided 95% CI for the proportion will be provided for each category.

15.8.2.6. Hematologic Parameters

Hematologic parameters (platelets, LDH, hemoglobin) will be summarized at baseline and each postbaseline time point using descriptive statistics for continuous variables for the observed value as well as the change from baseline. A MMRM with the fixed, categorical effect of visit and fixed, continuous effect of the specific test's baseline value as covariates may be fit to test whether changes differ from zero at each time point.

15.8.2.7. Hemoglobin Response

The number and proportion of patients with an increase from baseline in hemoglobin ≥ 20 g/L, observed at 2 separate assessments obtained at least 4 weeks (28 days) apart, and any measurement in between, will be summarized over time by presenting the number and proportion of responders along with a 2-sided 95% CI for each postbaseline time point.

15.8.2.8. Quality of Life

Quality of life will be evaluated using EQ-5D-3L (all patients; [Appendix E](#)), FACIT Fatigue version 4 Questionnaire (patients ≥ 18 years of age; [Appendix F](#)), and Pediatric FACIT Fatigue Questionnaire (patients < 18 years of age; [Appendix G](#)). The EQ-5D-3L and FACIT Fatigue data will be summarized at baseline and each postbaseline time point using descriptive statistics for continuous variables for the observed value as well as the change from baseline. A MMRM with the fixed, categorical effect of visit and fixed, continuous effect of the specific test's baseline value as covariates may be fit to test whether changes differ from zero at each time point.

15.9. Safety Analyses

All safety analyses will be performed for the Safety Set, defined for all patients who receive at least 1 dose of ALXN1210.

15.9.1. Adverse Events

The following definitions will be used for AEs:

- Pretreatment adverse events: Any AE that starts after providing informed consent, but before the first infusion of study drug
- Treatment-emergent adverse event: Any AE that starts during or after the first infusion of study drug. Adverse events that start 56 days or later after the last dose of study drug will not be considered as treatment emergent.
- Treatment-emergent SAE: A treatment-emergent AE (TEAE) that is serious ([Section 11.7.4](#) for definitions).

The incidence of TEAEs, TEAEs leading to withdrawal from the study, TEAEs leading to study treatment discontinuation, drug-related TEAEs, TEAEs during study drug administration, severe TEAEs, and SAEs will be summarized. All AEs will be coded using MedDRA version 18 or higher, and will be summarized by system organ class (SOC) and PT overall, by severity, and by relationship to treatment. Detailed by-patient listings of TEAEs, SAEs, related TEAEs, TEAEs during study drug administration, TEAEs leading to withdrawal from the study, and TEAEs leading to study treatment discontinuation will be provided.

15.9.2. Physical Examination and Vital Signs

Adverse changes from baseline in physical examination findings will be classified as AEs and analyzed accordingly.

Vital signs will be summarized descriptively at baseline and postbaseline time points and for changes from baseline.

By-patient listings will be provided.

15.9.3. Clinical Laboratory Tests

Observed values and changes from baseline in clinical chemistry, hematology, and urinalysis will be summarized descriptively at baseline, and at each postbaseline time point. For laboratory results that can be classified as normal, low, or high based on normal range values, shifts from baseline in classification will be summarized for all study visits.

15.9.4. Electrocardiograms

By-patient data listings of ECG parameters will be provided. Electrocardiograms will be evaluated and summarized as normal, abnormal not clinically significant, or abnormal clinically significant. A shift from baseline to worst on-study ECG table will be presented for ECG results. Observed values and change from baseline in ECG intervals (PR, RR, QT, and QTc) will be summarized descriptively at baseline and each postbaseline time point. QT interval will be corrected for heart rate using Fridericia's formula (QTcF).

15.9.5. Immunogenicity

Abnormal immunogenicity findings, including the incidence and titers for ADAs to ALXN1210 will be presented at each postbaseline time point in tabular format. The proportion of patients ever positive and the proportion of patients always negative may be explored.

15.10. Pharmacokinetic/Pharmacodynamic Analyses

Individual serum concentration data for all patients who receive at least 1 infusion of ALXN1210 and who have evaluable PK data will be used to derive PK parameters for ALXN1210.

Graphs of mean serum ALXN1210 concentration-time profiles will be constructed. Graphs of serum concentration-time profiles for individual patients may also be provided. Actual dose administration and sampling times will be used for all calculations. Descriptive statistics will be calculated for serum concentration data at each sampling time, as appropriate. Assessment of population-PK may be considered using data from this study or in combination with data from other studies.

The PD effects of ALXN1210 administered IV will be evaluated by assessing the absolute values and changes and percentage changes from baseline in free C5 serum concentrations over time, as appropriate. Assessments of PK/PD relationships may be explored using data from this study or in combination with data from other studies.

Pharmacodynamic analyses will be performed for all patients who receive at least 1 infusion of study drug and who have evaluable PD data. For PD parameters, summary tabulations of mean, SD, median, minimum, and maximum values will be presented for actual, change and percentage change from baseline. The relationship between changes in PD parameters, exploratory biomarkers, and the effects of treatment outcome may be evaluated.

15.11. Exploratory Analyses

15.11.1. Biomarker and APC Activity Analyses

For exploratory biomarker analyses, summary statistics will be presented for actual, change and percentage change from baseline.

The relationship between ALXN1210 concentration and exploratory biomarkers or the correlation between clinical benefit and key exploratory biomarkers may be assessed by graphical display. Exploratory analysis and potential relationships between clinical outcomes, PK/PD, genetic profile, and biomarker levels may also be performed. APC activity and autoantibody results will be summarized if evaluated.

15.11.2. Genetics

Exploratory genetics may be performed to investigate genetic variants in genes known to be associated with aHUS, as well as to identify novel genetic variants associated with aHUS, complement dysregulation, or metabolism or efficacy of ALXN1210.

15.11.3. Additional Signs or Symptoms of aHUS and Resource Utilization

Resource utilization will be assessed using the Resource Utilization Patient Questionnaire ([Appendix H](#)) and additional signs or symptoms of aHUS will be assessed using the Patient-reported aHUS Symptoms Questionnaire ([Appendix I](#)).

Resource Utilization Questionnaire data and Patient-reported aHUS Symptoms Questionnaire data will be summarized at baseline and each postbaseline assessment using discrete data summary statistics.

15.12. Other Statistical Issues

15.12.1. Missing or Invalid Data

If a Day 1 assessment is missing, the Screening assessment will be used as the baseline assessment.

For evaluation of Complete TMA Response during the 26-week Initial Evaluation Period (primary endpoint), patients missing an efficacy assessment that is part of the definition of Complete TMA Response while still on-study, will have their last observation carried forward (LOCF). For patients who will have terminated early from the study prior to Week 26, their data up to the time of discontinuation will be used to assess Complete TMA Response.

Missing data for QoL instruments will be handled as specified in the instructions for each instrument.

15.13. Interim Analyses

An interim analysis is planned for this study at the end of the 26-week Initial Evaluation Period after all patients have completed or withdrawn from the 26-week Initial Evaluation Period. Additionally, a second analysis to summarize long-term efficacy, safety, and PK parameters will be performed at the end of the 2-year Extension Period.

16. INFORMED CONSENT, ETHICAL REVIEW, AND REGULATORY CONSIDERATIONS

16.1. Informed Consent and Assent

The Investigator is responsible for ensuring that the patient understands the potential risks and benefits of participating in the study, including answering any questions the patient may have throughout the study and sharing in a timely manner any new information that may be relevant to the patient's willingness to continue his or her participation in the study.

The ICF will be used to explain the potential risks and benefits of study participation to the patient in simple terms before the patient is entered into the study, and to document that the patient is satisfied with his or her understanding of the risks and benefits of participating in the study and desires to participate in the study.

The Investigator is responsible for ensuring that informed consent is given by each patient or the patient's legal representative. This includes obtaining the appropriate signatures and dates on the ICF prior to the performance of any protocol procedures and prior to the administration of investigational product. The Investigator must retain the original version of the signed ICF. If the ICF is amended, the original signed, amended version must also be retained. A copy of the signed ICF(s) must be given to the patient.

As used in this protocol, the term "informed consent" includes all informed consent given by patients or, as applicable, informed consent by their legally authorized representatives if the patient is unable to provide informed consent.

16.2. Data Monitoring Committee

An independent Data Monitoring Committee (DMC) comprising experts in relevant biomedical fields who have no direct relationship with the study will be appointed by the sponsor. The DMC will review and evaluate the accumulated study data for patient safety and make recommendations on continuing study drug administration or termination of the study. The DMC will review study information on a regular basis as outlined in the DMC charter, which is maintained separately from the study protocol.

Final decisions regarding the conduct of the study will be made by the sponsor after consultation with the DMC. All appropriate regulatory authorities and Ethics Committees will be notified of any significant action.

Each member of the DMC will be required to sign a contract agreement, which includes a confidentiality and financial disclosure statement, assuring no conflicts of interest as a condition for membership on the committee.

The specific responsibilities of the DMC are described in the DMC Charter, which is maintained as a separate document.

16.3. Ethical Review

All ICFs must be compliant with the ICH guideline on GCPs.

Documentation of IRB/IEC approval of the protocol and the ICF must be provided to the sponsor before the study may begin at the investigational sites. The IRB/IEC(s) will review the protocol as required.

16.4. Regulatory Considerations

This study will be conducted in accordance with:

1. Consensus ethics principles derived from international ethics guidelines, including the Declaration of Helsinki and Council for International Organizations of Medical Sciences (CIOMS) International Ethical Guidelines
2. The ICH GCP Guideline [E6]
3. The ICH Clinical Trials of Medicinal Products in the Pediatric Population [E11]
4. Applicable national and local laws and regulations

The Investigator or designee will promptly submit the protocol to applicable IRB/IEC(s).

Some of the obligations of the sponsor will be assigned to a third-party organization.

An identification code assigned to each patient by the EDC system will be used in lieu of the patient's name to protect the patient's identity when reporting AEs and other study-related data.

16.4.1. Changes/Deviations to Protocol

The Investigator may need to deviate from the protocol to eliminate an immediate hazard to a trial subject without prior notification of the IRB/IEC. Any deviations from the protocol must be fully documented. The deviation and the reasons for it should be submitted to the IRB/IEC, Sponsor, and appropriate regulatory authority if required (ICH GCP E6 [R1] 4.5.4).

After the commencement of the clinical trial, the Sponsor may make changes to the protocol. If those changes are significant, the regulatory authority and applicable IRB/IEC will be notified.

16.5. Publication Policy

The full terms regarding publication of the results of this study are outlined in the applicable Clinical Study Agreement.

18. APPENDICES

APPENDIX A. COMMON CREATININE REFERENCE INTERVALS

Age (Gender) Group	97.5 th Percentile Value (mg/dL)	97.5 th Percentile Value (μmol/L)
11 to < 13 years of age	0.71	63
13 to < 15 years of age	0.81	72
15 to Adult (males)	1.18	104
15 to Adult (females)	1.02	90

Source: Adapted from [Panteghini, 2008](#); [Ceriotti, 2008](#).

APPENDIX B. ANTIBODY MEDIATED REJECTION CRITERIA

The revised (Banff 2013) classification of acute/active antibody-mediated rejection in renal allografts will be used to assess antibody mediated rejection. All 3 features must be present for diagnosis.

Criteria^{a,b,c}
Histologic evidence of acute tissue injury, including one or more of the following:
Microvascular inflammation (g score > 0 ^d and/or ptc score > 0)
Intimal or transmural arteritis (v score > 0) ^e
Acute thrombotic microangiopathy, in the absence of any other cause
Acute tubular injury, in the absence of any other apparent cause
Evidence of current/recent antibody interaction with vascular endothelium, including at least one of the following:
Linear C4d staining in peritubular capillaries (involving at least 10% of ptc by immunofluorescence on frozen sections, or any ptc by IHC on paraffin sections)
At least moderate microvascular inflammation (sum of g and ptc scores ≥ 2) ^f
Increased expression of gene transcripts in the biopsy tissue indicative of endothelial injury, if thoroughly validated ^g
Serologic evidence of donor-specific antibodies (HLA or other antigens)

Source: [Haas, 2014a](#)

^a For all antibody-mediated rejection (ABMR) diagnoses, it should be specified in the report whether the lesion is C4d-positive [involving $\geq 10\%$ of ptc by immunofluorescence on frozen sections or any ptc by immunohistochemistry (IHC) on paraffin sections] or without evident C4d deposition (< 10% of ptc by immunofluorescence on frozen sections; completely negative by IHC on paraffin sections).

^b These lesions may be clinically acute, smoldering, or subclinical. Biopsies showing 2 of the 3 features, except those with donor specific antibody (DSA) and C4d without histologic abnormalities potentially related to AMR or cell-mediated rejection (the latter seen mainly in ABO-incompatible renal allografts) may be designated as ‘suspicious’ for acute/active ABMR.

^c Modified from [Haas, 2014b](#).

^d Recurrent/de-novo glomerulonephritis should be excluded.

^e It should be noted that these arterial lesions may be indicative of ABMR, T-cell-mediated rejection (TCMR), or mixed ABMR/TCMR. Arterial lesions are only scored in arteries having a continuous media with 2 or more smooth muscle layers.

^f In the presence of acute TCMR, borderline infiltrates, or evidence of infection, ptc score at least 2 alone is not sufficient to define moderate microvascular inflammation, and glomerulitis must be present (g score ≥ 1).

^g At present, the only validated molecular marker meeting this criterion is ENDAT expression, and this has only been validated in a single center (University of Alberta). The use of ENDAT expression at other centers or other test(s) of gene expression within the biopsy as evidence of ABMR must first undergo independent validation as was done for ENDAT expression by [Sis, 2009](#).

APPENDIX C. MANAGEMENT OF POTENTIAL DRUG INFUSION REACTIONS

Infusion of other monoclonal antibodies has been associated with infusion reactions, with onset typically during or shortly after completion of the infusion. For this reason, patients will be carefully observed during each infusion.

Patients who develop AEs of rash, hives, itching, or dysphagia of mild to moderate intensity during their infusion of ALXN1210 may continue to receive the infusion if deemed to be medically appropriate by the Investigator. Medical intervention may include, but is not limited to, slowing of the infusion rate (with or without treatment) or interrupting or stopping the infusion.

Any acute reaction should be treated according to standard medical practice depending upon clinical signs and symptoms. If a patient requires medical intervention, the patient should remain at the investigational site until his or her condition stabilizes. The AE and any associated concomitant medications must be captured on the patient's source document and eCRF.

Some patients treated with IV infusions of monoclonal antibodies have experienced concurrent reactions with signs or symptoms that can be classified as acute allergic reactions/hypersensitivity reactions or cytokine release syndrome. Signs and symptoms include headache, fever, facial flushing, pruritus, myalgia, nausea, chest tightness, dyspnea, vomiting, erythema, abdominal discomfort, diaphoresis, shivers, hypertension, lightheadedness, hypotension, palpitations, and somnolence. Anaphylaxis might occur at any time during an infusion; therefore, patients will be monitored closely during the infusion. In addition, the re-administration of some monoclonal antibodies has been associated with serum sickness-like reactions manifesting 1 to 14 days after drug administration. All AEs that may indicate an infusion-related response will be graded according to CTCAE Version 4.03 or higher.

Before any infusion is started, the treating physician and other appropriate personnel must make certain that medication (ie, adrenaline, inhaled beta agonists, antihistamines, corticosteroids) and other equipment to treat anaphylaxis are readily available. The infusion must be stopped immediately if Grade ≥ 2 allergic/hypersensitivity reactions (including drug fever) or Grade ≥ 3 cytokine release syndrome/acute infusion reaction occurs. The sponsor must be notified within 24 hours of any infusion reaction requiring interruption or discontinuation of study drug.

Patients who experience a reaction during the administration of study drug should be treated according to institutional guidelines. For a Grade 1 or Grade 2 infusion reaction, the infusion should be temporarily stopped and treatment with an antihistamine (eg, diphenhydramine 25 to 50 mg orally [PO] or equivalent) and acetaminophen (650 mg orally or equivalent) may be considered. If the patient's signs and symptoms have resolved (with or without administration of the above medication), the infusion may be restarted. However, the patients should be infused at a slower rate and be monitored closely for any signs and symptoms of infusion reactions during the remainder of the infusion. Patients experiencing an infusion reaction should be observed in the clinic until resolution of the reaction, or until the Investigator determines the patient is no longer at risk. Patients who experience a severe reaction during administration of study drug resulting in discontinuation of study drug should undergo all scheduled safety, PK, and PD evaluations required by the protocol.

If anaphylaxis occurs according to the criteria listed below, then administration of subcutaneous epinephrine (1/1000, 0.3 to 0.5 mL, or equivalent) should be considered. In the case of bronchospasm, treatment with an inhaled beta agonist also should be considered. Patients administered an antihistamine for the treatment or prevention of an infusion reaction should be given appropriate warnings about drowsiness and impairment of driving ability before being discharged from the center.

Table 9: Clinical Criteria for Diagnosing Anaphylaxis

Anaphylaxis is highly likely when any 1 of the following 3 criteria is fulfilled:
1. Acute onset of an illness (minutes to several hours) with involvement of the skin, mucosal tissue, or both (eg, generalized hives, pruritus or flushing, swollen lips-tongue-uvula), and at least 1 of the following: a. Respiratory compromise (eg, dyspnea, wheeze-bronchospasm, stridor, reduced peak expiratory flow (PEF), hypoxemia) b. Reduced blood pressure (BP) or associated symptoms of end-organ dysfunction (eg, hypotonia [collapse], syncope, incontinence)
2. Two or more of the following that occur rapidly after exposure to a likely allergen for that patient (minutes to several hours): a. Involvement of the skin-mucosal tissue (eg, generalized hives, itch-flush, swollen lips/tongue/uvula) b. Respiratory compromise (eg, dyspnea, wheeze/bronchospasm, stridor, reduced PEF, hypoxemia) c. Reduced BP or associated symptoms (eg, hypotonia [collapse], syncope, incontinence) d. Persistent gastrointestinal symptoms (eg, crampy abdominal pain, vomiting)
3. Reduced BP after exposure to known allergen for that patient (minutes to several hours): a. Systolic BP of less than 90 mm Hg or greater than 30% decrease from that person's baseline

Source: [Sampson, 2006](#)

Abbreviations: BP= blood pressure; PEF = peak expiratory flow

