11.7.2. Severity Assessment

The severity of AEs will be graded using Common Terminology Criteria for Adverse Events (CTCAE) version 4.03 or higher. A grading (severity) scale is provided for each AE term. Each CTCAE term is a Lowest Level Term (LLT) per the Medical Dictionary for Regulatory Activities (MedDRA[®]). Each LLT will be coded to a MedDRA preferred term (PT).

Grade refers to the severity of the AE. The CTCAE assigns a grade of 1 through 5, with unique clinical descriptions of severity for each AE ([Table 7](#)).

Table 7: Adverse Event Severity Grading Scale

Grade	Description
Grade 1	Mild; asymptomatic or mild symptoms; clinical or diagnostic observations only; intervention not indicated
Grade 2	Moderate; minimal, local or noninvasive intervention indicated; limiting age-appropriate instrumental activities of daily living (ADL) ^a
Grade 3	Severe or medically significant, but not immediately life-threatening; hospitalization or prolongation of hospitalization indicated; disabling; limiting self-care ADL ^b
Grade 4	Life-threatening consequences; urgent intervention indicated.
Grade 5	Death related to AE.

Abbreviations: ADL = activities of daily living; AE = adverse event

^a Instrumental ADL refers to preparing meals, shopping for groceries or clothes, using the telephone, managing money, etc.

^b Self-care ADL refers to bathing, dressing and undressing, feeding self, using the toilet, taking medications, and not bedridden.

Any change in the severity of an AE should be documented based on specific guidelines in the eCRF Completion Guidelines.

Severity and seriousness must be differentiated: severity describes the intensity of an AE, while the term seriousness refers to an AE that has met specific criteria for a SAE as described in [Section 11.7.4](#).

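### Appendix C lets an infusion continue through mild to moderate rash, hives, itching or dysphagia, but elsewhere says to stop it for reactions of the same grades

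*Protocol*

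**What the plan says.** Three statements in protocol Appendix C bear on the same signs.

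- **Named-sign permission.** For rash, hives, itching or dysphagia of mild to moderate intensity during the infusion, patients "may continue to receive the infusion if deemed to be medically appropriate by the Investigator". The interventions then listed as possible include "slowing of the infusion rate (with or without treatment) or interrupting or stopping the infusion".
- **Immediate stop.** "The infusion must be stopped immediately if Grade ≥ 2 allergic/hypersensitivity reactions" occur, with drug fever counted among them, or if "Grade ≥ 3 cytokine release syndrome/acute infusion reaction occurs".
- **Temporary stop.** "For a Grade 1 or Grade 2 infusion reaction, the infusion should be temporarily stopped". The same paragraph allows a restart at a slower rate, with close monitoring, after signs and symptoms have resolved.

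Appendix C has events that may indicate an infusion-related response graded by CTCAE. Table 7 in Section 11.7.2 labels Grade 1 as mild and describes Grade 2 as "Moderate; minimal, local or noninvasive intervention indicated". Appendix C also requires the sponsor to be told within 24 hours of an infusion reaction that needs study drug to be interrupted or discontinued.

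**The concern.** The permission is worded by intensity and the two stop instructions by grade. Once Table 7 links the two scales, an investigator watching moderate hives develop can find one sentence that allows the infusion to go on and another that forbids it. A site could rely on the first in good faith and breach a mandatory safety instruction a few paragraphs later.

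The 24-hour notice depends on the same choice. An infusion that is continued has not been interrupted, so the same event may prompt a notice from one site and none from another.

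The setting makes clear wording more important. Section 8 plans about 55 patients at about 200 sites, and SAP Section 7.2.1.3 expects very few patients per center. Many sites will therefore have little experience with this drug and will rely on the written rule.

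**Working it through.** No figure in the plan is in question, so the check compares the wording grade by grade. The inputs are the three Appendix C statements and the Table 7 labels (mild is Grade 1, moderate is Grade 2).

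| Event during infusion | Named-sign permission | Temporary stop | Immediate stop | Result |
|---|---|---|---|---|
| Grade 1, one of the four signs, regarded as an infusion reaction | may continue | should stop, may restart | does not apply | conflict |
| Grade 2, one of the four signs, regarded as an infusion reaction and judged allergic | may continue | should stop, may restart | must stop, silent on restart | conflict, and restart unclear |
| Grade 2, one of the four signs, regarded as an infusion reaction but not judged allergic | may continue | should stop, may restart | does not apply | conflict |
| Grade 1, other signs only (for example flushing) | does not apply | should stop, may restart | does not apply | one instruction |
| Grade 2, other signs only, not allergic | does not apply | should stop, may restart | does not apply | one instruction |
| Grade 2 drug fever | does not apply | should stop, may restart | must stop, silent on restart | agree on stopping, restart unclear |
| Grade 3 or higher, allergic or acute infusion reaction | does not apply | does not apply | must stop | one instruction |

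Three steps lie behind the table.

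1. *Can the four signs be allergic reactions in the protocol's own terms?* Appendix C's list of signs for allergic/hypersensitivity reactions or cytokine release syndrome includes pruritus and erythema, and Table 9 names generalized hives among the skin signs of anaphylaxis. The overlap is therefore plausible. It still needs the investigator to classify the event as allergic.
2. *Do the two stop sentences contradict each other?* Not on the act of stopping: an infusion can be stopped at once and restarted later. They differ in force (must against should) and on restart, which only the temporary-stop paragraph addresses. The immediate-stop sentence sets its threshold for an acute infusion reaction at Grade 3, although Grades 1 and 2 already call for a temporary stop. This may mean that a different kind of stop is intended, but the text does not say so.
3. *Is the matter settled elsewhere?* Section 9.5 only refers back to Appendix C. Section 8.3.2 covers permanent discontinuation after a serious infusion reaction and does not address whether an infusion continues through a Grade 1 or 2 event. Appendix C's references to standard medical practice and institutional guidelines do not rank the three statements.

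For exposure, dosing on Days 1, 15, 71 and 127 gives 4 infusions per patient in the Initial Evaluation Period. That is 55 × 4 = 220 planned infusions if all 55 patients complete it, with further infusions every 8 weeks in the Extension Period. The documents give no rate of infusion reactions, so the number of infusions affected cannot be estimated.

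**The case against.** The strongest reply is that the permission is conditional and discretionary. It lists interruption and stopping among the options, so a site that stops the infusion breaches none of the three statements. This stands, and it rules out one stronger reading. A reader might infer three mutually exclusive orders, so that no site could comply. The documents do not support that, because the permission is simply wider than the directives that follow. The reply does not remove the problem, since a site that uses the permission as written can breach a directive.

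A second reply is that the three statements concern different kinds of event. Table 7 is a generic scale, and Section 11.7.2 notes that CTCAE describes severity separately for each term. A moderate skin sign is therefore not automatically a Grade 2 allergic reaction. This also stands, and it is why the mandatory stop is taken to apply only where the event is judged allergic. However, Appendix C does not define the three event terms relative to one another, so a site has no stated basis for separating them.

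A reader might also infer that every Grade 1 or 2 skin or allergic reaction is caught. The table shows otherwise, because the permission names four signs only. Nor do the documents show a conflict with the Pharmacy Manual. Section 9.1 cites it for packaging, storage, preparation, administration and disposal, and nothing indicates that it contains rules for managing reactions.

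**Conclusion.** The inconsistency is real but narrow. It concerns rash, hives, itching and dysphagia at Grades 1 and 2, where continuation is permitted in one place and a stop is called for in another. A smaller gap accompanies it: whether the restart allowed after a Grade 1 or 2 infusion reaction also covers a Grade 2 allergic reaction. The conclusion rests on the Table 7 link between intensity and grade, and on the sign being regarded as an infusion reaction or, for the mandatory stop, an allergic one.

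A reader might go on to infer that the efficacy result is compromised. The documents do not support that. The primary analysis counts complete TMA responders over the FAS, and neither definition refers to whether an infusion was interrupted. Adverse events are recorded and summarized either way, including those starting during administration. What can vary between sites is the interruption itself, the 24-hour notice, and the action-taken entry in the adverse event listings (SAP Section 7.3.2.1). No document shows how often this would happen.

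The wording should be corrected because it is a safety instruction that applies at every infusion and is cheap to put right.

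**What to change.** The sponsor's clinical team should reconcile the Appendix C paragraphs. The revised text should:

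- define how the four named signs, an allergic/hypersensitivity reaction and an infusion reaction relate to one another;
- state which instruction takes precedence, so that each CTCAE grade and reaction type has a single instruction;
- state whether the restart provision covers a Grade 2 allergic reaction.

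The content of each instruction is a clinical decision for that team. The cost is a protocol clarification and a letter to sites. The sample size and the planned analyses do not change.
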